1.1 Specific Aims

- 1) **To determine whether there is a difference in best spectacle-corrected visual acuity (BSCVA) at 6 months between patients receiving ultrathin DSAEK and DMEK.** We hypothesize that the DMEK group will have improved visual acuity compared with DSAEK at 3 months, but not at 6 months. By randomizing 25 patients per arm, we anticipate 80% power to detect a one standard deviation, or approximately 1.2 Snellen lines, difference in BSCVA between the DMEK and DSAEK groups.
- 2) **To evaluate endothelial cell loss at 6 months between patients receiving ultrathin DSAEK and DMEK.** We hypothesize that there will be a difference in endothelial cell loss at 6 months between patients receiving ultrathin DSAEK and DMEK, accounting for pre-operative endothelial cell count.
- 3) **To assess the relative role of light scatter, higher-order aberrations and graft thickness on visual acuity.** We predict that there will be increased light scatter at the

graft-host interface and but no difference in posterior corneal higher-order aberrations of the central 4mm in DSAEK versus DMEK.¹⁰

While long-term outcomes such as graft rejection and survival are beyond the scope of the initial phase of this study, we anticipate we will be able to evaluate these as we follow patients at 12 and 24 months.

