3. PATIENT FLOW

3.1 Study Timeline

The enrollment period will be 24 months. Study participants will be required to have follow-up visits at months 3 (visit window: 2-4 months), 6 (visit window: 5-7 months), 12 (visit window: 10-14 months), and 24 (visit window: 20-28) from the time of surgery. Additional visits may be needed and will be determined by the surgeon/investigator.

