4.3 Examinations During Follow-up Visits

There will be 4 follow-up visits for this study – Month 3, 6, 12, and 24; all of these visits would be expected in normal post-operative care. During each follow-up appointment, tests will be done on the participant's study eye; these include: BSCVA, intraocular pressure (IOP), corneal thickness using a Pachymeter, manifest refraction, slit lamp and slit lamp photography, endothelial imaging, Pentacam topography and densitometry, and optical coherence tomography (OCT) testing. Dilated retinal exam will be performed at the discretion of the surgeon.

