Descemet's Endothelial Thickness Comparison Trial

Statistical Analysis Plan

Francis I. Proctor Foundation, University of California San Francisco
Casey Eye Institute, Oregon Health & Science University
Byers Eye Institute, Stanford University

Investigators:

[name], PhD¹
[name], PhD*²
[name]*²
[name]*³
[name], COT²
[name], MS¹

*Principal Investigator

¹Casey Eye Institute, Oregon Health & Science University, Portland, Oregon

² Francis I. Proctor Foundation, University of California San Francisco, San Francisco, California

³Byers Eye Institute, Stanford University, Palo Alto, California

DETECT Statistical Analysis Plan

Table of Contents

1. Background	1
2. Sample Size and Randomization.....	1
3. Baseline Characteristics	1
4. Primary Analysis.....	1
5. Secondary Analyses	1
6. Other Data.....	2

1. Background

Descemets Endothelial Thickness Comparison Trial (DETECT) is a randomized, double-masked, two-arm clinical trial. The purpose of this study is to determine which of two types of corneal transplant surgeries has the better visual outcome. Study participant's eyes will be randomized to one of two treatment groups – 1.) Ultrathin Descemet's Stripping Endothelial Keratoplasty (DSAEK) or 2.) Descemet's Membrane Endothelial Keratoplasty (DMEK).

2. Sample Size and Randomization

We anticipate that 25 eyes per arm would provide 80% power to detect a 0.12 logMAR difference (approximately 1.2 Snellen lines), assuming two-tailed alpha, and a standard deviation of best spectacle-corrected visual acuity (BSCVA) at 6 months of 0.12 logMAR (approximately 1.2 Snellen lines) at 6 months. Participant's eyes will be randomized using random block sizes in Microsoft Excel ([name]).

3. Baseline Characteristics

Baseline characteristics between the 2 arms will be compared using Fisher exact test for categorical variables and Wilcoxon rank sum test for continuous variables.

4. Primary Analysis

For the primary study analysis, we will compare BSCVA between the two groups at the 6-month time period (between 5-7 months) using ANCOVA, with baseline BCVA and treatment group as covariates. Statistical significance will be assessed by permutation with a two-sided alpha of 0.05. (If the correlation coefficient between baseline BCVA and 6 month BCVA has magnitude less than 0.1, we will omit the variable entirely, yielding a post-test only analysis).

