As a methodological sensitivity analysis, we will conduct ANCOVA with ranks (which becomes the Wilcoxon rank sum test in the post-test only case). Model checking will be conducted for the primary analysis (and for all secondary analyses) based on analysis of residuals versus fitted values. We will conduct leave-one-out influence analysis to locate highly influential observations (a procedure we will apply to secondary analyses also). Individuals with missing six month data will be included based on last observation carried forward from the 3 month records; individuals with no follow-up data cannot be included but will be tabulated. Sensitivity analysis of missing values will be conducted to assess the range of values of missing observations that would be needed to change the results of the hypothesis test.

Protocol for measuring BCSVA is outlined in the MOP. BSCVA will be analyzed using an intent to treat analysis, with all eyes that are randomized being analyzed at 6 months regardless of subsequent surgery or graft failure. We will tabulate results by study site.

One safety analysis will be performed. No interim efficacy or futility analysis will be conducted.

5. Secondary Analyses

Key secondary outcomes

- We will analyze endothelial cell counts controlling for baseline endothelial cell count measured at the eye bank using mixed effect multiple linear regression conducted
- NEI-VFQ will be compared between the two groups with multiple linear regression, controlling for baseline VFQ.
- Three-month BCVA will be analysed using the same procedure as the primary outcome.
- A linear mixed model will be used in which both three and six month data are modeled, with a random intercept for eye, and with time, baseline BCVA, and treatment assignment as fixed effects. A graft rejection episode will be defined as loss of graft clarity due to edema with evidence of inflammation such as anterior chamber cell or keratic precipitates, and will be compared between the two groups using Fisher's exact test.
- For the purposes of this study, primary graft failure will be defined as a lack of graft clearing or need for re-graft within the first 2 months, and will be compared between the two groups using Fisher's exact test.

Supplementary secondary outcomes

- A pre-specified non-inferiority threshold is set at a 0.1 logMAR difference in visual acuity.

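### The primary analysis fills missing 6-month BSCVA with the 3-month value, which shifts the result towards DMEK under the protocol's own hypothesis; the shift is small unless missingness and the early gap are both large

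*SAP*

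**What the plan says.** SAP section 4 compares 6-month BSCVA (window 5-7 months) by ANCOVA with baseline acuity and treatment. "Statistical significance will be assessed by permutation with a two-sided alpha of 0.05". The primary rule for missing values is: "Individuals with missing six month data will be included based on last observation carried forward from the 3 month records". Eyes with no follow-up are left out and tabulated. The section also states: "BSCVA will be analyzed using an intent to treat analysis, with all eyes that are randomized being analyzed at 6 months".

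Protocol section 1.1 gives the expected course: "We hypothesize that the DMEK group will have improved visual acuity compared with DSAEK at 3 months, but not at 6 months". Under Protocol section 3.1 the 3-month visit may fall anywhere from month 2 to month 4.

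Other planned elements bear on the point:

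- SAP section 4 has a sensitivity analysis that asks what missing values would overturn the test result.
- SAP section 4 has a baseline rule: "If the correlation coefficient between baseline BCVA and 6 month BCVA has magnitude less than 0.1, we will omit the variable entirely".
- SAP section 4 has a rank-based check: "As a methodological sensitivity analysis, we will conduct ANCOVA with ranks".
- SAP section 5 has a separate 3-month comparison. It also has a mixed model of both visits with time, baseline, treatment and a random intercept per eye, and no treatment-by-time term.
- SAP section 5 has a supplementary LOCF rule for eyes that are re-grafted. That rule is distinct from the one discussed here.

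**The concern.** The estimate is meant to describe month 6, but an eye without a 6-month value contributes one from month 2 to 4. This would be harmless if the treatment difference were the same at both visits. The protocol expects it not to be: a DMEK advantage early and none at 6 months. LOCF then imports part of the early advantage into the comparison that is expected to be null.

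The primary estimate and p-value are at stake. The permutation test does not protect against this. It keeps its level if the arms differ at neither visit and missingness is unrelated to arm, but the hypothesised scenario has a difference at 3 months.

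**Working it through.** **Inputs.** From SAP section 2: 25 eyes per arm, SD 0.12 logMAR, design difference 0.12 logMAR. From SAP section 4: two-sided alpha 0.05. Not in the documents, so assumed and ranged: share missing (5%, 10%, 20%) and 3-month gap d3 (0.06 and 0.12 logMAR).

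**The plan's own figure.** On these inputs a two-sample t test has 93.4% power (94.2% by normal approximation), not the stated 80%. An SD of 0.148 (t test) or 0.151 (normal approximation) would give 80%. That is a separate matter. It is used here only to justify SD 0.151 as a second value.

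**Size of the shift.** Let both arms have mean m at 6 months. Let gS and gM be the mean gains from 3 to 6 months in DSAEK and DMEK, so that d3 = gS - gM. Let pS and pM be the shares missing, unrelated to acuity. After LOCF the arm means in logMAR are m + pS x gS and m + pM x gM. The shift towards DMEK is

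pS x gS - pM x gM = pS x d3 + (pS - pM) x gM,

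which is p x d3 when pS = pM = p.

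**Type I error, equal random loss.** SE = 0.12 x sqrt(2/25) = 0.0339. The rejection rate is P(|Z + bias/SE| > 1.96). The simulation used 10,000 trials and 499 label permutations. Assumed correlations were 0.3 (baseline with follow-up) and 0.6 (3 with 6 months), and the 3-month value was always observed. The Monte Carlo error is 0.2-0.5 points.

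| d3 | Missing | Bias towards DMEK | LOCF, formula | LOCF, simulated | Observed-only ANCOVA, simulated | Proposed model, simulated |
|---|---|---|---|---|---|---|
| 0.06 | 5% | 0.003 | 5.1% | 5.3% | 5.1% | 5.1% |
| 0.06 | 10% | 0.006 | 5.4% | 5.2% | 4.7% | 4.6% |
| 0.06 | 20% | 0.012 | 6.4% | 6.4% | 5.3% | 5.0% |
| 0.12 | 5% | 0.006 | 5.4% | 5.6% | 5.1% | 5.1% |
| 0.12 | 10% | 0.012 | 6.4% | 7.0% | 5.2% | 5.3% |
| 0.12 | 20% | 0.024 | 10.9% | 10.8% | 4.8% | 4.8% |

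A second simulation with correlations 0.5 and 0.7 and a t test gave 11.4% for LOCF in the last row. With SD 0.151 (SE 0.0427) and d3 0.12, the formula gives 5.2%, 5.9% and 8.7%. At SD 0.12 the type I error reaches 10% when p x d3 is about 0.022, for example 18% missing with d3 0.12 or 37% with d3 0.06.

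**Unequal loss (d3 0.12, gM 0.05).**

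- DSAEK 5%, DMEK 20%: 0.05 x 0.12 - 0.15 x 0.05 = -0.0015, so slightly towards DSAEK. Simulated type I error 5.0%.
- DSAEK 20%, DMEK 5%: 0.20 x 0.12 + 0.15 x 0.05 = 0.0315 towards DMEK. Simulated type I error 13.6%.

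**Loss depending on 3-month acuity** (d3 0.12, gM 0, logistic slope +1 or -1 per SD). LOCF bias is 0.009-0.019 at 10% missing and 0.018-0.036 at 20%. Type I error is 6.1-7.6% and 7.8-14.8%. Observed-only ANCOVA is biased by 0.004-0.007 towards DSAEK.

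In all these scenarios the proposed model had bias of at most 0.001 logMAR and type I error of 4.6-5.3%.

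**The planned mixed model.** Without a treatment-by-time term it estimates one effect for both visits. With complete data, a gap of 0.12 at 3 months and none at 6, that effect is (0.12 + 0)/2 = 0.06. At correlation 0.6 its SE, ignoring baseline, is 0.0339 x sqrt((1 + 0.6)/2) = 0.0304. It would therefore be declared significant about half the time, and it does not isolate month 6.

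**The case against.** The strongest reply concerns weight. Neither document gives a missing rate or a 3-month gap, and the hypothesis gives only a direction. Attendance should be good: willingness to attend is an inclusion criterion, and Protocol section 4.3 says of the follow-up visits that "all of these visits would be expected in normal post-operative care". At 10% missing or less, equal in both arms, the bias is at most 0.012 logMAR, a tenth of the design difference. The 10.9% needs 5 of 25 eyes missing per arm and an early gap of a full SD that vanishes by month 6. Direction is not certain either. All of this stands, and it limits the size of the point.

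The SAP also plans an analysis of how extreme the missing values must be to change the result, and a 3-month comparison that would show an early gap. A reader could therefore see that LOCF mattered. That is true, but the primary estimate and p-value would still be built on LOCF.

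The comparison above also suits the proposed model, because every loss mechanism simulated was random or depended on observed data. In a check with about 10% loss per arm (d3 0.12, 4,000 trials), DSAEK loss depended on poor 6-month acuity and DMEK loss was random. Mean bias towards DMEK was +0.009 for LOCF, -0.008 for the model and -0.012 for observed-only ANCOVA. When DSAEK eyes with good acuity were lost instead, LOCF was worse than the model (+0.019 against +0.008). So the model's advantage does rest on data missing at random.

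Finally, the simulations treat eyes as independent and permute labels freely, although a participant may enrol both eyes and allocation is blocked. Those are separate issues that the planned ANCOVA shares.

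**Conclusion.** The concern holds and should be fixed. Under the protocol's hypothesis, with equal loss unrelated to acuity, the primary rule biases the 6-month contrast towards DMEK by the share missing times the 3-month gap. At 5-10% missing this is 0.003-0.012 logMAR, with type I error of 5.1-6.4% by formula. It becomes serious only when both factors are large: 0.024 logMAR and about 11% at 20% missing with a gap of 0.12. If DSAEK eyes are lost more often it can be larger; if DMEK eyes are lost more often it can cancel or reverse. These sizes rest on assumed missing rates, gaps and correlations. The algebra does not.

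**What to change.** Take the primary 6-month contrast from a likelihood-based model of the observed 3- and 6-month BSCVA, with treatment-by-time and baseline-by-time terms and an unstructured two-visit covariance. Permute treatment labels using the studentised 6-month contrast, and state that this is exact only if there is no effect at either visit. With complete data the estimate equals the planned ANCOVA estimate. Every eye with a 3-month value stays in, as the intent-to-treat sentence intends.

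Linked text needs a line each:

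1. Apply the correlation rule to eyes with an observed 6-month value. If it is met, drop baseline and baseline-by-time.
2. Run the rank ANCOVA on observed 6-month values and repeat it on the LOCF data.
3. Take the 3-month result from the same model's 3-month contrast.
4. Apply the planned missing-value sensitivity analysis to the new primary analysis.
5. Label the secondary random-intercept model as an average over both visits.

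Keep 3-month LOCF as a named sensitivity analysis, separate from the re-graft LOCF in section 5. Also state whether an acuity taken outside 5-7 months counts as missing.

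**Cost.** No new data are needed. The model relies on data missing at random, and it loses power against LOCF when the effect is 0.12 at both visits (simulated):

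| SD | Missing | LOCF | Proposed model | Observed-only ANCOVA |
|---|---|---|---|---|
| 0.12 | 10% | 94.9% | 93.1% | 92.0% |
| 0.12 | 20% | 95.0% | 91.1% | 89.0% |
| 0.151 | 10% | 81.3% | 77.7% | 75.9% |
| 0.151 | 20% | 80.0% | 72.8% | 70.1% |

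If the SD is really 0.151, power falls below 80%. At 20% missing the model's loss is then 4 to 9.5 points for assumed 3-to-6-month correlations of 0.8 to 0.4.

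**Simpler alternative.** Run the planned ANCOVA on observed 6-month values, with LOCF as a sensitivity analysis. Items 1-3 then stay almost as written, and the estimate is unbiased under completely random loss. It drops eyes seen only at 3 months, has the lowest power of the three, and shows the small bias given above when loss depends on 3-month acuity.

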3.2 Eligibility Requirements

3.2.1 Study Area

Recruitment of eligible participants will be done at the Casey Eye Institute and Byers Eye Institute. Eligible participants will be screened by the primary surgeon and research staff at OHSU and Stanford. Potential participants will be approached during a standard of care clinical visit in the outpatient practice of the primary investigator at Casey Eye Institute, OHSU. These are patients that need to have corneal surgery whether or not they participate in this study.

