3.3 Randomization

Each study eye will be randomly assigned to the 1) DSAEK or 2) DMEK treatment group. Block randomization will be performed using a computer program (Statistical package R; Version 2.12; R Foundation for Statistical Computing, Vienna, Austria) by the coordinating site.

Once an eye is enrolled in the study, the study coordinator will assign the study participant's eye an ID (alpha-numeric code) and inform the eye bank (Note: The eye bank will assign tissue to the study participant prior to knowing which arm the study participant is assigned to). The eye bank will then sign into the Dropbox account associated with this study, open the "New Patient" folder, and then open the file named with the particular study participant ID.

Once the eye bank has opened the file, the study eye has been assigned a study participant ID and randomized to treatment group; therefore, they will be included in the intention to treat analysis. (Note: See eye bank protocol for full donor tissue procurement and assignment information).

The treatment assignment will not contain identifiable patient information and will be shared using a password that is only known by the eye bank. The eye bank may only open the document for a given study participant and not for past or future study participants. The treatment assignment document should be moved from the "New Patients" folder to the "Old Patients" folder once opened.

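### The primary ANCOVA has no site term and the SAP does not tie the permutation test to the allocation blocks, at some cost in precision

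*SAP*

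**What the plan says.** **Sites and time.** Protocol 3.2.1 names two recruiting centres: "Recruitment of eligible participants will be done at the Casey Eye Institute and Byers Eye Institute". Protocol 1.3 gives a 24-month enrolment period.

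**Allocation.** Protocol 3.3 says "Block randomization will be performed using a computer program (Statistical package R; Version 2.12"; SAP section 2 says "eyes will be randomized using random block sizes in Microsoft Excel". Both describe blocked allocation. Neither gives the block sizes or says whether the list was stratified by site, and they name different software.

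**Primary test.** SAP section 4 compares 6-month BSCVA "using ANCOVA, with baseline BCVA and treatment group as covariates". Baseline is dropped if its correlation with the 6-month value is below 0.1 in magnitude. Then: "Statistical significance will be assessed by permutation with a two-sided alpha of 0.05". No permutation scheme follows.

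**Role of site.** The only mention in the analysis is "We will tabulate results by study site". None of the listed sensitivity analyses (ranks, leave-one-out, missing values) adjusts for site. The 3-month analysis in SAP section 5 copies the primary procedure.

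**The concern.** Site is known for every eye and is needed for the planned table, yet the model ignores it. If 6-month acuity differs between the two centres beyond what baseline acuity explains, that difference is counted as noise when the arms are compared.

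The permutation scheme matters for a related reason. A permutation test should reproduce the way treatment was assigned. Blocking keeps the arms balanced over calendar time (and within site, if the list was made by site), so a slow drift in outcomes largely cancels between arms. A reference distribution from free shuffling of all labels lacks that balance and is too wide. Because the SAP is silent, two analysts could both follow it and report different primary p-values.

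What is at stake is precision with 25 eyes per arm. Lost precision makes a non-significant 6-month result more likely, and no difference at 6 months is what Protocol 1.1 hypothesises. It also widens the interval to be read against the 0.1 logMAR non-inferiority threshold in SAP section 5.

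**Working it through.** **1. The plan's own figure.** Inputs from SAP section 2: 25 eyes per arm, difference 0.12 logMAR, SD 0.12 logMAR, two-tailed. The alpha value is missing there, so 0.05 is taken from section 4. The standardised effect is 0.12/0.12 = 1. The t-test power is 93.4% (94.2% by the normal approximation), not the stated 80%. That discrepancy is a separate matter; 93.4% is the reference point below.

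**2. Variance saved by a site term.** Let f be the smaller site's share of 50 eyes and d the site difference remaining after baseline adjustment, in within-site SDs. Both are assumptions, with f from 0.2 to 0.5 (10 to 25 eyes). Residual degrees of freedom go from 47 to 46, so

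ratio (with site / without) = [1 / (1 + f(1−f)d²)] × 47/46

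- d = 0: 47/46 = 1.022, a cost of 2.2%.
- d = 0.5: f = 0.2 gives (1/1.04) × 1.0217 = 0.982; f = 0.5 gives (1/1.0625) × 1.0217 = 0.962. Saving 1.8% to 3.8%.
- d = 1: f = 0.2 gives (1/1.16) × 1.0217 = 0.881; f = 0.5 gives (1/1.25) × 1.0217 = 0.817. Saving 11.9% to 18.3%.

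Interval width scales with the square root: about 1-2% narrower at d = 0.5 (√0.982 = 0.991, √0.962 = 0.981) and 6-10% at d = 1 (√0.881 = 0.939, √0.817 = 0.904).

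**3. Power at the SAP's 0.12 logMAR effect.** The SAP does not say whether its SD of 0.12 is within-site or total. Taking it as within-site, the SD without a site term is √(0.0144 + f(1−f)D²), where D is the site difference in logMAR. With a site term it is 0.12.

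| D (logMAR) | Split | SD without site | Power without site | Power with site |
|---|---|---|---|---|
| 0.03 | 70:30 | 0.1208 | 93.1% | 93.4% |
| 0.06 | 70:30 | 0.1231 | 92.2% | 93.4% |
| 0.12 | 70:30 | 0.1320 | 88.3% | 93.4% |
| 0.06 | 50:50 | 0.1237 | 91.9% | 93.4% |
| 0.12 | 50:50 | 0.1342 | 87.3% | 93.4% |

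At D = 0.06 the gain is 1.2 to 1.4 points (50:50 unrounded: 93.37 − 91.93 = 1.44). At D = 0.12 it is 5.1 to 6.1 points. If 0.12 is the total SD, power without site stays at 93.4% and a site term raises it to 94.5-94.7% at D = 0.06 (1.1 to 1.3 points) and 97.4-97.9% at D = 0.12 (4.0 to 4.5 points). These powers do not charge the lost degree of freedom, so at D = 0.03 the net gain is about nil.

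**4. Permutation scheme.** Simulated ANCOVA permutation test with 50 eyes and assumed random blocks of 2, 4 or 6. Drift is linear over enrolment; site difference and drift are assumed; power is at 0.12 logMAR.

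| Blocks; site difference; drift | | Free, no site | Within block, no site | Free, site | Within block, site |
|---|---|---|---|---|---|
| Not by site; 0.12; 0 | Type I | 0.051 | 0.047 | 0.049 | 0.047 |
| | Power | 0.887 | 0.886 | 0.940 | 0.934 |
| Not by site; 0.12; 0.12 | Type I | 0.040 | 0.050 | 0.035 | 0.046 |
| | Power | 0.899 | 0.905 | 0.935 | 0.939 |
| By site; 0.12; 0.12 | Type I | 0.024 | 0.049 | 0.040 | 0.046 |
| | Power | 0.881 | 0.927 | 0.909 | 0.927 |

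Simulation error is up to about half a point on type I error and one point on power. Three things follow. Free permutation is conservative under drift, and more so when blocks are also nested in site. Within-block permutation alone does not recover the site loss unless blocks are nested in site (0.905 against 0.899 in the middle scenario). A site term recovers most of it, and using both keeps type I error closest to 0.05 under drift.

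**The case against.** Leaving site out of a small two-centre ANCOVA while tabulating by site is a defensible prespecified choice. The test remains valid, power at 0.12 logMAR stayed above the SAP's 80% target in every scenario run, and for moderate site differences the gain is close to the 2% cost. Baseline acuity may already absorb part of any case-mix difference between centres. All of that stands, and it keeps the point minor.

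Four stronger readings are tempting but unsupported.

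- A reader might take site to stand for surgeon. Protocol 3.2.1 says only "Eligible participants will be screened by the primary surgeon and research staff at OHSU and Stanford", and no passage available for review gives the number of surgeons per site. Nor are the two eye banks in Protocol 4.2 linked to site.
- A reader might infer that a free shuffle will be used. The SAP is silent, and its wording is compatible with re-randomising within blocks, so the drift loss is conditional on the scheme chosen.
- A reader might call a chance site imbalance a bias. Without stratification, the arms would differ in site share by 20 points or more in about 7-26% of allocations (10 to 25 of 50 eyes at the smaller site). With a 0.06 logMAR site difference this moves the estimate by 0.20 × 0.06 = 0.012 logMAR. That is ordinary randomisation variability, already covered by the test's error rate.
- A reader might infer a large power loss from a steep learning curve. The documents give no time trend to support one.

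**Conclusion.** The point holds as a minor one about efficiency and specification. The primary model omits a recorded design variable, and the permutation scheme, which defines the primary test, is not stated. The consequence is some lost precision and, if labels are shuffled freely, a conservative test; it is neither bias nor excess false positives.

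The size depends entirely on assumed site differences and drift. It is negligible to small up to half an SD between sites and becomes noticeable only near a full SD. The drift figures also assume the block sizes. Whether within-block permutation helps with site variation depends on whether the list was made by site, which the documents do not say.

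**What to change.** In SAP section 4, and by reference for the 3-month analysis:

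1. Add study site as a fixed effect in the ANCOVA, kept whether or not baseline BCVA is dropped under the correlation rule.
2. State that the permutation distribution is generated by re-randomising within the allocation blocks actually used, nested in site only if the list was made by site.
3. State whether the list was stratified by site, and reconcile R (Protocol 3.3) with Excel (SAP section 2) so that the list to be used is identified.

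The cost is one degree of freedom (about 2% of variance if sites do not differ) and slightly more programming. No new data are needed: site is already recorded and the blocks belong to the allocation list. The wording should be settled before anyone sees outcomes by arm.

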1.2 Study Outcomes

Primary Outcome:

- BSCVA at 6 months

Secondary Outcomes:

- Endothelial cell counts
- Corneal higher-order aberrations as measured by Pentacam
- Interface haze as measured by Pentacam densitometry
- Change in NEI-VFQ *from baseline to 3 months and 12 months*
- Primary graft failure, defined as a lack of graft clearing or need for re-graft within the first 2 months
- Graft rejection, defined as loss of graft clarity due to edema with evidence of inflammation such as anterior chamber cell or keratic precipitates.

Other Outcomes measured:

- Refraction
- Graft thickness as measured by OCT and pachymetry
- Operative times
- Adverse events/Complication rates

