3.4 Study Visits

3.4.1 Baseline Visit

During this visit, eligible patients who are enrolling for the first time will be enrolled in the study and will give consent. The baseline patient form will be completed and the NEI-VFQ will also be administered. If a patient includes a second eye in the study, they will complete an abbreviated baseline patient form for that study eye prior to surgery. They will not complete a second NEI-VFQ at the baseline visit for their second eye. Patients will also complete BSCVA, IOP, Pachymetry, and Pentacam tests at baseline.

3.4.2 *Surgery Visit*

The enrolled study participant's eye(s) will undergo either DSAEK or DMEK surgery. If both of a participant's eyes are included in the study, randomization to DSAEK or DMEK will be performed independently for each eye.

3.4.3 *Follow-Up Visits*

The follow-up patient form will be completed at each visit, for each enrolled eye. Data collected for each follow-up visit will include:

3 month follow-up: BSCVA, IOP, pentacam topography and densitometry pachymetry, optical coherence tomography, and endothelial imaging will be performed. The NEI-VFQ form will also be completed

6 month follow-up data: BSCVA, IOP, pentacam topography and densitometry pachymetry, optical coherence tomography, endothelial imaging, and slit-lamp photography will be performed.

12 month follow-up: BSCVA, IOP, pentacam topography and densitometry pachymetry, optical coherence tomography, and endothelial imaging will be performed. The NEI-VFQ form will also be completed

3.4.4 *Final Visit*

During the Month 24 final visit, the final status and follow-up patient forms will be completed. BSCVA, IOP, pentacam topography and densitometry pachymetry, optical coherence tomography, and endothelial imaging will also be performed.

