4.2 Treatment

For each procedure, the tissue will be prepared by either Lions VisionGift or Sightlife. Each participant will undergo surgery only once and will take approximately 1-2 hours. This study requires 6 visits to the clinic over a period of 2 years, there may be additional post-operative visits (above what the study requires) following this surgical procedure.

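### The study schedule (Protocol Table 1) omits the Month 3 NEI-VFQ that Protocol 1.2 and 3.4.3 require

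*SAP*

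**What the plan says.** **Protocol 1.2 (Study Outcomes)** lists, among the secondary outcomes, change in NEI-VFQ "from baseline to 3 months and 12 months".

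**Protocol 3.4.3 (Follow-Up Visits)** says of the 3-month visit, and again of the 12-month visit: "The NEI-VFQ form will also be completed". The 6-month entry has no such sentence.

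**Protocol 4.4, Table 1** has a row for NEI-VFQ with two marks: pre-op (limited to the first eye) and Month 12. The Month 3 cell is blank.

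**SAP section 5** places NEI-VFQ among the key secondary outcomes and gives one sentence: "NEI-VFQ will be compared between the two groups with multiple linear regression, controlling for baseline VFQ". Protocol section 8 defers all statistical detail to the SAP.

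On units, SAP section 1 says "Study participant's eyes will be randomized to one of two treatment groups". Protocol 3.4.2 says that, where both eyes are enrolled, "randomization to DSAEK or DMEK will be performed independently for each eye". Of participants who add a second eye, Protocol 3.4.1 says: "They will not complete a second NEI-VFQ at the baseline visit for their second eye".

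**The concern.** Table 1 is the schedule that a site coordinator is likely to work from. If it is followed as printed, half of the follow-up data for the only patient-reported outcome listed will not be collected. A questionnaire about current visual function cannot be completed retrospectively.

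Month 3 also matters for participants with two study eyes. The visit windows are "months 3 (visit window: 2-4 months), 6 (visit window: 5-7 months), 12 (visit window: 10-14 months". Second-eye surgery that precedes a first-eye Month 3 score (taken by month 4) also precedes the first-eye Month 12 score (taken from month 10). The reverse is not true. For first-eye scores, Month 3 is therefore the time point less mixed with second-eye surgery, and it is the one that the table leaves out. This does not extend to scores timed from a second eye's own surgery, which all follow both operations.

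**Working it through.** No planned figure is attached to NEI-VFQ (no sample size, power or target difference), so there is nothing to reproduce. The check is a comparison of passages, followed by a short calculation on the two-eye question.

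**1. Time points, side by side**

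| Source | Baseline | Month 3 | Month 6 | Month 12 | Month 24 |
|---|---|---|---|---|---|
| Protocol 1.2 | yes | yes | no | yes | no |
| Protocol 3.4.1, 3.4.3 and 3.4.4 | yes | yes | no | yes | no |
| Protocol Table 1 | yes (first eye) | **blank** | blank | yes | blank |
| SAP section 5 | yes (covariate) | not stated | not stated | not stated | not stated |

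The sources differ in one Table 1 cell, and the SAP names no follow-up time point.

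**2. Could this be a text-extraction fault?** The row splits cleanly into the six visit columns, and its second mark falls on Month 12, where Protocol 3.4.3 also puts the form. A shifted or dropped mark is unlikely, though not excluded.

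**3. Does another visible passage repair it?** Protocol 4.3 lists the follow-up tests and does not mention NEI-VFQ. Protocol 10.1 names a study visit checklist held as a separate document. It may list the Month 3 form; we cannot tell.

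**4. What the SAP leaves open.** It does not say whether a row is an eye or a participant, which arm a participant with one eye in each arm belongs to, or which baseline a second eye takes. The first-eye limit on the baseline form is a collection rule and settles none of these.

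**5. Can the effect of leaving this open be sized?** Inputs: 50 eyes, 25 per arm (SAP section 2). The number of two-eye participants, B, is not given; 3, 6, 10 and 15 are assumed. Take eyes as rows and all scores after both surgeries.

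- *Score is the average of the two eyes.* Write tau for the effect on one eye. The unoperated fellow eye counts in the average, so a one-eye participant's score moves by tau/2, and a second operated eye adds another tau/2. The effects add. Given one eye's arm, the fellow study eye is in the same arm with probability 24/49 and in the other with 25/49. The eye-level arm difference, relative to the one-eye effect, is 1 + (2B/50) × (24/49 − 25/49) = 1 − (2B/50)/49, or 0.998, 0.995, 0.992 and 0.988. There is almost no attenuation.
- *Score follows the better eye.* The result depends on the unoperated eye. In a simulation with an assumed eye SD of 0.5 and effect of 0.3, the ratio is 0.94, 0.88, 0.80 and 0.70 if that eye is always worse. It is 0.98, 0.97, 0.94 and 0.90 if that eye equals the study eye on average. It exceeds 1 (1.06 to 1.35 over the four values of B) if that eye is better on average.
- *B = 0.* The ratio is 1.

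Even the direction is therefore not fixed by the documents.

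**The case against.** **The table mismatch is clerical.** Protocol 1.2 and 3.4.3 agree and are explicit, only the summary table differs, and sites may work from the checklist. This stands as a limit on the harm, which is possible and not shown. It does not remove the contradiction. The table is the operative visit schedule, and the lost data could not be recovered.

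**The SAP gap is missing detail, not an error.** This stands. Two-eye participants may also be few: Protocol 4.2 says "Each participant will undergo surgery only once", and Protocol 1.1 counts patients, not eyes, per arm. Against that, Protocol 3.4.1 and 3.4.2 plainly provide for second eyes. The point remains a request for a stated rule.

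**A stronger reading is tempting.** A reader might infer that a participant with one eye in each arm must dilute the arm difference substantially, and that averaging over two eyes shows this. It does so only if the score ignores the fellow eye until that eye is operated on, which neither document says. Once the fellow eye is counted, averaging is the additive case above. Only a better-eye score departs materially from 1, in a direction set by fellow-eye status.

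**A stronger remedy is also tempting:** restricting the main comparison to scores taken before second-eye surgery. That selects on an event after randomisation, discards rows and brings no power gain. The documents give no ground for requiring it.

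**Conclusion.** Table 1 contradicts Protocol 1.2 and 3.4.3 on the Month 3 NEI-VFQ and should be corrected. At stake is one of two follow-up time points of a key secondary outcome, if sites follow the table and the checklist does not list the form. This rests on the table having been read correctly from the PDF, which is likely.

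The SAP's silence on time point, unit and two-eye rule is a minor, secondary matter. Two analysts could follow its sentence faithfully and use different rows, arms and baselines. No size can be attached to this: it depends on how the score weights the two eyes, on fellow-eye status and on the unknown number of two-eye participants. The primary BSCVA analysis is unaffected.

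**What to change.** **Protocol 4.4, Table 1:** add an X for NEI-VFQ at Month 3, so that the table agrees with Protocol 1.2 and 3.4.3. Confirm that the study visit checklist lists the form at Months 3 and 12. The cost is one table cell and one check.

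**SAP section 5 (minor):** extend the NEI-VFQ sentence to name the 3-month and 12-month scores and to state the unit of analysis and the two-eye rule. One workable rule is one row per participant at each time point, with the arm of the first-enrolled eye, the baseline taken before the first surgery, and all first-eye rows kept. Limiting the analysis to scores before second-eye surgery should be a sensitivity analysis at most. Another rule would close the gap equally well if it is fixed before the data are seen. The cost is about two sentences; only the optional sensitivity analysis needs the surgery and questionnaire dates.
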